\mathbf{Q} is a vector representing the secular time effect, where q_{jmk} is the calendar quarter; and, the time elapsed since encounter $j-1$; for $j=2,\dots$

In addition

A_{ikm} is a vector of random effects, $[A_{1km},\dots,A_{5km}]$ specified as varying across patients nested within clusters

$$A_{ikm} \sim [A_i + \alpha_{ikm} + \gamma_{im}]; \quad i=1,\dots,6$$

$$[\alpha_{ikm}] \sim N(0, \Sigma_\alpha)$$

$$[\gamma_{im}] \sim N(0, \Sigma_\gamma)$$

where Σ s are exchangeable correlation matrices.

μ_{imw} , $i=1,\dots,6$ is a discrete-time vector of random effects for each cluster m and step w ; and,

ν_{it} , $i=1,\dots,6$ is a multivariate autoregressive process of order 1, AR(1) with Gaussian noise, to account for time dependent correlation of responses within each patient over time; and,

Prior to estimating this model, the distributions of the SPPADE scores will be examined and, if appropriate, transformed to have approximately normal distributions. Covariates will be similarly reviewed and either transformed or categorized before inclusion in the model.

In general, fitting the above models (1) which has several random effects (in both time and across clusters) can be challenging. However, Markov Chain Monte Carlo estimation is very effective at fitting such models and are appropriate for assessing stepped-wedge cluster randomized designs.⁹⁹ Moreover, by incorporating historical time trends into our priors for the effect of calendar time, a Bayesian model can increase statistical power relative to a frequentist approach.¹⁰⁰ All other priors will be flat. In the event that model (1) can't be estimated, we will simplify the error structure and other features using review of variable distributions and correlations, including intra-cluster correlations and time dependent correlation, to inform the simplifications. Then, using our final model we will calculate posterior probabilities and credible intervals to assess whether coefficients differ from zero; specifically, we will achieve the primary aim of the study by calculating the posterior probabilities that each of B_1, \dots, B_6 is greater than 0; we will accept that the intervention is effective if $PP[\text{abs}(B_i) > 0, i=1,\dots,6] \geq 0.80$.

In the event that the model with patient surveys as the unit of analysis cannot be computed, we will use an alternative cluster-period model for the primary analysis. We will aggregate outcomes and covariates for each cluster for each time period and use these cluster-level estimates to assess the effect of the intervention. We will calculate the mean of each of the 6 different SPPADE NRS scores collected during trial cluster-periods. We will also calculate the mean baseline score for each participant that reports one or more ePROMs. We will then test the first primary hypothesis using a multivariate regression model using these 15 clusters \times 6 period = 90 cluster-period values, including an indicator for intervention status for each cluster-period, and adjusting for mean baseline scores and including indicators for study step to account for secular trends and for indicators for cluster to account for cancer type. We will adjust for cluster-period averaged values of factors of patients reporting during each period for which the SMD between intervention and control cluster-periods are >0.2 .

To assess the robustness of using the CP model, we will replicate the main analyses for each symptom NRS score. We will use the originally specified generalized mixed effects model, as well as the CP model adapted to the univariate dependent variable. This former model will be estimated at the survey level, with random effects for surveys within patients and patients within clusters; these 6 models (one for each symptom score) also included all pre-specified patient covariates, baseline symptom score, the lag in weeks since the baseline measurement and the interaction of the lag time with the baseline effect.

Because there is potential for the intervention to impact the baseline scores as well, we will replicate the cluster-period and survey level models each symptom score, including patients with only 1 survey score.

We will estimate models using the STAN software package.

Hypotheses H1b

To test whether the intervention has a differential effect on those patients with at least one elevated symptom score,

we will construct an indicator, E_{ijkm} , varying by measurement time, which indicates whether the i^{th} prior symptom score was elevated (>3). By interacting these indicators with the main intervention effects B_i we can assess the impact of the intervention on the corresponding scores of patients with at least one elevated score:

$$Y_{ijkm} = A_{ikm} + B_i X_{jkm} + C E_{ijkm} + D_i E_{ijkm} X_{jkm} + L_i(t) Y_{i[j-1]km} + F Z_k + D S_m + Q q_{jmk} + \mu_{imw} + \nu_{it} \quad ; \quad i=1, \dots, 6 \quad (2)$$

We will then test the hypothesis as above by calculating the $PP[\text{Abs}(D_i) > 0, i=1, \dots, 6]$

In the event that the model with patient surveys as the unit of analysis cannot be computed to test Hypotheses H1b, we will use the cluster-period approach outlined for testing H1a, but will summarize SPPADE NRS scores for each cluster-period according to whether the patient had any prior elevated scores; we will then estimate a model analogous to the cluster-period model used to test Hypothesis H1a but including an indicator for post-elevation and the interaction with the intervention indicator.

Finally, as a secondary objective of this aim, to better understand the effectiveness of different components of the E2C2 intervention in reducing symptoms, we will perform a separate set of analyses to assess the impact of specific process measures (D.2.d) on SPPADE scores and other clinical outcomes. For each process measure we will first examine the distribution of values (frequency or duration) and, if highly skewed, categorize into 2 or more categories. We will then estimate for each outcome a mixed effects linear model with a random cluster effect, where the outcome is the dependent variable and the main independent variable is the continuous or categorized process measure, adjusting for patient covariates as described above. By testing for an overall process measure effect, we can assess which processes contribute most to reducing outcomes; we will also report measures of variance explained to enable relative comparison of process measure effects.

Specific Aim 2 Analyses. We will summarize patient characteristics (sex, age, insurance status) by intervention status (baseline, intervention). We will also summarize all survey responses by cluster implementation status, including clinician characteristics (age, sex, years of practice). All patients will be analyzed on an intention to treat status; this principle will be extended to the cluster status, so that delays in implementation of an intervention will not affect the intervention status of patients.¹⁰¹ All methods will account for correlation of outcomes within clusters and across patients. As a secondary objective of this aim, we will assess the change in clinician survey constructs over time. This analysis will include each clinician with at least two completed surveys at least 6 months apart.

As in Aim 1, we will also assess the effect of process measures on SPPADE scores and other clinical outcomes. We will use models appropriate for count data, selecting standard or zero-inflated Poisson or negative binomial models according to Aikake's Information Criteria, or logit models for binary measures. For each outcome we will estimate a) bivariate models including only one survey score; b) a model with all scores; and c) a final model which also includes clinician characteristics.

Aim 3

Endpoints

Primary:

SPPADE and physical function NRSs will serve as both the E2C2 primary outcome and a critical component of the E2C2 intervention since NRS scores populate the EHR algorithms that determine whether patients are triaged to Level 1 or 2,

and whether patients are offered specific intervention components (education, medications, etc.). Patients will complete NRSs for SPPADE symptoms and physical function prior to medical oncology clinic appointments at all stages of the trial, i.e., prior to and after E2C2 initiation. ePROs will be more frequently administered to symptomatic patients outside of their appointment-linked assessments as part of the intervention. *To avoid potential bias from oversampling of symptomatic patients, only SPPADE symptom NRSs collected in association with clinic appointments will be included in the primary analysis.*

NRSs. Simple 11-point NRSs have been used for decades in the assessment of diverse latent traits among patients with cancer of all types and stages.¹⁰²⁻¹⁰⁴ These single-item assessments have been the most often-used QOL and symptom measures in National Cancer Institute (NCI) cancer control clinical trials,¹⁰⁵ and they feature prominently in the most reliable and valid symptom assessment tools, both generic and cancer-specific.^{106,107} The NRSs utilized in E2C2 to assess the SPPADE symptoms and physical function will be patterned on the extensively validated MD Anderson Symptom Assessment Scale and Edmonton Symptom Assessment Scale with respect to the 24 hour recall period, and verbal anchors identical to the, e.g., "No pain" and "Worst possible pain," respectively.^{108,109} NRSs have been shown to be more responsive than either Likert or verbal rating scales,¹¹⁰ and preferred by patients over visual analogue scales.¹¹¹

Secondary:

PROMIS CATs. Depression, anxiety, pain, and physical function will be assessed with the PROMIS CATs (www.promis.org). In addition to strong endorsement by the NIH,^{112,113} use of CATs is justified because IRT-based instruments have generally better discrimination across the entire trait range than legacy PROs, being less prone to floor and ceiling effects.^{114,115} Moreover, administering IRT-modeled banks with CATs enhances the efficiency and precision of measurement relative to short forms.^{116,117} The PROMIS item banks utilized in E2C2 have been validated, with robust IRT calibration across different clinical populations.¹¹⁸⁻¹²⁰

Health care utilization. Healthcare utilization for E2C2 will consider health care encounters including hospitalizations, ED visits, ICU admissions, clinic outpatient visits, and calls to the oncology care team. EHR entries and administrative billing data will be aggregated to construct a comprehensive data set of all clinical encounters. Data collected for hospitalizations will include admission and discharge diagnoses, length of stay, ICU admission/transfer, and whether an admission was planned for anti-cancer treatment or unplanned, and if the latter, initiated from the ED or an office visit. For ED encounters, we will capture diagnoses and whether an encounter resulted in hospital or ICU admission. Clinic visits will be captured using billing data which will include CPT codes, ICD-10 codes, location, and clinician NPI numbers. We will be able to ascertain clinician discipline and specialty from the NPI numbers. Calls to the oncology care team are not billed but are reliably captured in the EHR. A recent audit established that 87% of calls to medical oncology practitioners were recorded in the EHR, and that rates of capture did not vary systematically across disciplines. However, call characteristics, e.g., duration, were not reliably recorded. Therefore we will use count data in analyses to model call frequency.

We will estimate mixed effects Poisson regression models with utilization events during the trial period as dependent variables. Because utilization events will be available for all trial participants, we will perform analyses with cohorts comprised of all trial participants and those who completed ≥ 1 ePROM, and ≥ 2 ePROMs.

The majority, but not all, of patients' health care utilization will occur at MC facilities. Established patterns suggest that 75% to 80% of patients care will occur at an MC facility and that this frequency will not vary across E2C2 clusters, or phases of the E2C2 intervention, e.g., pre-E2C2, Stage 1. However, we will perform analyses that include only patients residing within driving distance of a trial site to assess the impact of distance. Additionally, we will use imputation methods and sensitivity analyses to assess the impact of mis-ascertainment of utilization data.

Cancer treatment adherence. The literature does not offer a definitive definition of cancer treatment adherence, even

for medications, or clarify which of the many candidate measures should be considered.¹²¹ We will therefore assess adherence broadly and examine the frequency of missed imaging, medical oncology clinic visits, and chemotherapy appointments. Additionally, we will capture any unplanned hiatuses in cancer treatment or dose reductions. This information is routinely recorded on electronic chemotherapy administration forms from which discrete structured data elements can be abstracted. For oral hormonal regimens we will use the accepted definition of at least 80% of recommended doses to create a binary variable.¹²² [name] (E2C2 Co-I) has contributed seminally to the literature on adherence to breast cancer adjuvant therapies.^{123,124} We will apply this criterion to oral chemotherapy and immunotherapy as well.

Vital status. Vital status will be verified through death certificates, the Mayo Clinic EMR, next-of-kin reports, the Mayo Clinic Tumor Registry and the Social Security Death Index website.

Reporting mode and rates. Patient reported outcomes will be collected via several modes for the E2C2 trial. These include remote modes; the patient portal and interactive voice response, and point of care modes; tablets and provider entry via Epic Care. Data regarding patients' mode of PRO reporting are automatically stored by the Epic EHR. We will perform descriptive statistics to characterize how reporting modes differ across subgroups defined by demographic, clinical, cancer-related, and symptom characteristics. Additionally, we will create uni- and multi-variate mixed models to estimate associations of reporting frequency and mode with patient characteristics.

Receptivity to receipt of symptom support. The E2C2 intervention provides low and high touch support for moderate and severe symptoms, respectively. Patients who endorse moderate symptoms (4-6/10) are offered the option to receive symptom self-management education materials for specific symptoms, Sleep disturbance, Pain, Anxiety, Depression, Fatigue, and Deficits in physical function. Similarly, patients who endorse severe symptoms (7-10/10) are offered the opportunity to discuss the same symptoms with a nurse symptom care manager. We will calculate descriptive statistics to characterize patients' preferences with regard to receipt of symptom support in subgroups defined by symptom type and intensity, as well as the stability of their preferences for symptom support. Additionally, we will estimate associations between patients' demographic and clinical characteristics and their interest in receiving support by constructing multivariate mixed models.

BIBLIOGRAPHY AND REFERENCES CITED

1. [name] AL, Shen T, Chang M, Basford JR. Appropriateness of the treatment of fatigued patients with stage IV cancer. *Support Care Cancer* 2013;21(1):229-33. DOI: 10.1007/s00520-012-1515-7.

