E2C2 / 18-007779

Enhanced, EHR-facilitated Cancer Symptom Control (E2C2)
Pragmatic Clinical Trial

NCT03892967

Document Date: 03/04/2025

IRB Minimal Risk Protocol Template

General Study Information

Principal Investigator: [name], MSCE

Study Title: Enhanced, EHR-facilitated Cancer Symptom Control (E2C2) trial

Protocol version number: March 4, 2025 Version 24

Research Question and Aims

Hypothesis: Collaborative care management for control of moderate or worse sleep disturbance, pain, physical function impairment, anxiety, depression, fatigue (SPPADE symptoms), and physical dysfunction among cancer survivors and patients with cancer will improve quality of life, symptom severity, and adherence to cancer treatment, and will also reduce need for acute care.

Aims:

Specific Aim 1. Conduct a cluster randomized pragmatic trial with a stepped wedge design to test the hypothesis that a symptom control-focused E2C2 intervention will significantly reduce SPPADE symptom and physical dysfunction scores; reduce unplanned hospitalizations, emergency department (ED) visits, and intensive care unit (ICU) admissions; improve adherence to cancer therapies; and improve self-reported quality of life.

H1a. SPPADE symptom scores will improve more, relative to prior scores, for patients who have been exposed to the intervention when compared with the improvement of patients that are not exposed.

H1b. Among patients who report moderate or worse symptoms, SPPADE symptom scores will improve more for patients who have been exposed to the intervention when compared with the improvement of patients that are not exposed.

Specific Aim 2. Evaluate the hypothesis that use of a multifaceted, evidence-based implementation strategy to support adoption and use of the E2C2 system will result in improvements in implementation and clinical outcomes.

Specific Aim 3. Conduct a mixed methods evaluation to detect, understand and reduce disparities in the adoption and implementation of the E2C2 intervention among elderly and rural-dwelling patients with cancer.

Background:

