We will summarize patient-, cluster-, and survey-level characteristics (e.g., sex, age, cancer type and stage, insurance status) by intervention status (pre-E2C2, E2C2) of the encounter. All analyses will be conducted on an intention to treat basis. The primary analysis will test differences in change in joint SPPADE symptom NRS scores in all participants, and in those who report elevated (4-10/10) symptoms, between participants who are exposed to the intervention and those who are not. We have two primary hypotheses. The first will assess the effect of the intervention across the full cohort of patients enrolled, Hypothesis *H1a*. The second will assess the effect of the intervention among patients who report moderate or worse symptoms, Hypothesis *H1b*. The rationale for Hypothesis *H1b* is that some intervention components are only offered to participants who report elevated symptom scores. Additionally, a large proportion of the trial cohort will only report mild or no symptoms. Among these participants there is little or no opportunity to improve symptoms and no practical exposure to the intervention. The original hypotheses regarding population-level effects will retain primary importance, yet it is critical to test intervention effects in the subset of patients that ever have elevated symptom scores.

We will include a common set of variables in all models testing the effectiveness of the intervention. Cancer type and stage will be included, as well as 7 variables selected as likely to impact the use of the portal and completion of the

[figure not shown]

Figure 3. Power simulations for E2C2 Interventions

surveys: from the EHR we will capture age (categorized into 10-year increments), sex (male or female), and severity of illness (Elixhauser score as a categorical variable). We will also link the patient 9-digit zip code to Census data to get estimates of educational level, income, and broadband access, which will be categorized into quartiles.

Hypotheses H1a

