To test the primary hypothesis H1a for our primary outcomes, we will use generalized linear mixed models to assess the effects of the intervention on each of the 6 SPPADE scores⁹⁰. All models will account for correlation of outcomes within clusters and across patients, and for changes in this correlation over time. We will adjust for time, measured by study period, to account for temporal effects. Each score will be adjusted for the prior score, with a coefficient that depends on the time t since the prior score; to account for potential changes in correlation of outcomes by over time we will include autoregressive terms at the patient level.⁹¹ To account for changing correlation within clusters over time we will incorporate a discrete-time correlation structure.⁹⁸

Our primary analysis will treat each SPPADE score as a continuous variable and employ a mixed effects generalized multivariate model; we will model all 6 scores jointly, which will allow us to account for the correlation between them and avoid correcting for multiple hypothesis tests.

Specifically, let Y_{ijkm} be the i^{th} score ($i=1,\dots,6$) of the j^{th} encounter for the k^{th} patient in the m^{th} cluster ($m=1,\dots,15$), for $j = 2,\dots$; the first score for each patient ($j=1$) is a baseline score collected during the first visit, not an outcome. Let $w=1,\dots,6$ indicate the trial step during which the survey is collected.

Then to test the hypothesis that the intervention impacts the 6 symptom scores we will estimate the joint models:

$$Y_{ijkm} = A_{ikm} + \mathbf{B}_i X_{jkm} + \mathbf{L}_i(t) Y_{i[j-1]km} + \mathbf{F} \mathbf{Z}_k + \mathbf{D} \mathbf{S}_m + \mathbf{Q} q_{jmk} + \mu_{imw} + \nu_{it} \quad ; \quad i=1,\dots,6 \quad (1)$$

where

X_{jkm} is an intervention indicator which equals 1 if encounter j for patient k in cluster m was post intervention and 0 otherwise;

\mathbf{B}_i is a vector of fixed effects for the intervention on symptom score i , $i = 1,\dots,6$;

\mathbf{L}_i is a vector of time dependent lags, representing the effect of the most recent measurement on the current one, as a function of time t in days between measures;

\mathbf{Z}_k is a vector of patient factors for patient k , \mathbf{F} is a corresponding vector of fixed effects;

\mathbf{S}_m is a cluster level set of indicators for randomization strata, \mathbf{D} is a vector of fixed effects;

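### H1b's model (2) picks its symptomatic group from scores that E2C2 may already have changed, so the estimate mixes effect with selection and needs a fixed-group sensitivity analysis

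*Combined protocol and SAP*

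**What the plan says.** The aims (Research Question and Aims, H1b) give the hypothesis as "Among patients who report moderate or worse symptoms, SPPADE symptom scores will improve more for patients who have been exposed to the intervention", without saying when a patient counts as symptomatic. Specific Aim 1 Analyses names it as one of two primary hypotheses and gives the reason: "it is critical to test intervention effects in the subset of patients that ever have elevated symptom scores".

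The timing is set in Hypotheses H1b. The indicator E_ijkm is "varying by measurement time, which indicates whether the" i-th "prior symptom score was elevated (>3"). It enters model (2) alongside the prior score as covariate: "By interacting these indicators with the main intervention effects" gives the coefficient D_i (not the strata coefficients, for which the plan also uses D). The stated purpose is "To test whether the intervention has a differential effect on those patients with at least one elevated symptom score", so the test is on D_i. The total effect in symptomatic patients, B_i + D_i, is not named as a result.

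If model (2) cannot be computed, the cluster-period fallback groups scores differently, "according to whether the patient had any prior elevated scores". Hypotheses H1a describes each patient's first score (j = 1) as one that "is a baseline score collected during the first visit, not an outcome". The H1b section has no analysis in which the group is fixed at that score or before go-live.

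**The concern.** From a patient's second exposed survey onward, the score that decides membership was recorded under the intervention. If pain falls to 3 or below at the first E2C2 visit, the next survey no longer counts as symptomatic for pain. A patient who does not respond stays in and contributes a symptomatic row each time. Under usual care E2C2 causes no such sorting. The two sets of symptomatic surveys can therefore hold different kinds of patient, although the randomisation of clusters to sequences was sound.

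The plan itself expects this movement. Triage to Level 1 or 2 lets patients change state with response, onset and worsening, and it treats non-response as a route to Level 2. The plan also guards against related problems elsewhere. Under Endpoints, it drops scores collected outside appointments so that symptomatic patients are not oversampled. Under Hypotheses H1a, it repeats models because first scores may be affected by the intervention. E_ijkm has no such check.

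At stake is the meaning of a primary result. An H1b estimate from model (2) alone cannot be separated into what E2C2 did and who remained in the group.

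**Working it through.** **1. The plan's own figure.** The Power Statement gives 70% power at 0.10 points and nearly 100% at 0.20 (level 0.05) for an effect on one symptom; it gives none for H1b. It prints no SD, covariance or cluster sizes, so the figures cannot be reproduced. They do fit each other (two-sided test assumed): SE = 0.10/(1.960 + 0.524) = 0.0403, and power at 0.20 = Φ(0.20/0.0403 − 1.960) = Φ(3.01) = 99.9%.

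**2. Does depletion occur, and how large is it?** Assumed, not from the documents: 0-10 rounded score, mean 3, between-patient SD 1.8, within-patient SD 1.7, AR 0.5, six follow-up surveys, half the patients exposed throughout. The benefit lasts once a patient is elevated and exposed. The average effect is held constant while the share of responders varies. The entries are the model (2) effect at E = 1, that is B + D (8 runs of 40,000 patients).

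| Average effect | All respond | 50% respond | 30% respond | Loss against all respond |
|---|---|---|---|---|
| 1.0 | -0.56 | -0.46 | -0.37 | 18%, 34% |
| 0.5 | -0.27 | -0.23 | -0.22 | 15%, 19% |
| 0.2 | -0.095 | -0.099 | -0.093 | none clear (Monte Carlo SE up to 0.004) |

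- Loss = 1 − (estimate / all-respond estimate), for example 1 − 0.37/0.56 = 34%.
- A run of the same design with 20 × 8,000 patients gave -0.582, -0.505 and -0.382 at 1.0 point: losses of 13% and 34%. Hence about 15-35%.
- At 0.5 points, two-decimal rounding makes the loss about 10-20%.
- With half responding (1.0 point), the responder share of exposed elevated rows fell from 50% at the first interval to 30% at the sixth. In usual care it stayed at 50%.
- For the tested coefficient, D_i went from -0.50 to -0.38 and -0.26 at 1.0 point (12 × 8,000): losses of 24% and 48%.
- With no effect, the estimate at E = 1 was -0.007 (Monte Carlo SE 0.005).

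**3. What is not depletion.** At 1.0 point the estimate is only about -0.58 when everyone responds. Much of the shortfall from -1.0 therefore comes from adjusting for a prior score that is itself exposed. The 30% case needs a 3.33-point drop in responders, which meets the floor of the scale. Grouping by first score also falls there, from -0.93 to -0.86. Scaling for this gives 1 − (0.382/0.86)/(0.582/0.93) = 29% rather than 34%.

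**4. Is the direction fixed?** A second simulation used five sequences, 60,000 patients and up to 8 surveys (mean 2.5, SDs 1.8 and 1.6, AR 0.4, mean effect -1.0). It compared model (2) with a group fixed by a first score above 3 before go-live. Model (2) is shown without / with a patient random intercept.

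| Pattern of benefit | Model (2), B + D | True effect, fixed group | Fixed-group fit |
|---|---|---|---|
| (a) Lasting, 40% respond | -0.48 / -0.59 | -0.76 | -0.74 |
| (b) Lasting, all respond | -0.65 / -0.71 | -0.79 | -0.76 |
| (c) Only after an elevated score, 40% respond | -0.71 / -0.92 | -0.43 | -0.49 |
| (d) As (c), all respond | -0.75 / -0.93 | -0.52 | -0.57 |
| (e) Builds with repeated offers | -0.85 / -0.85 | -0.94 | -0.79 |
| None | -0.01 / -0.01 | 0 | -0.03 |

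- In (a), model (2) is 37% or 22% below the fixed-group effect (1 − 0.48/0.76; 1 − 0.59/0.76).
- In (c), it is 65% or 114% above (0.71/0.43; 0.92/0.43).
- Two other variance settings kept these directions: (a) -0.45 to -0.62 against -0.65 to -0.84, and (c) -0.69 to -1.00 against -0.35 to -0.51.
- Selection is visible in (a). Of exposed elevated rows, 59% came from patients already offered E2C2 after an earlier elevated score (true effect -0.35) and 41% from patients not yet offered it (-0.92). The average is 0.59 × (-0.35) + 0.41 × (-0.92) = -0.58, against -0.76 in the fixed group.
- In (c), the true effect in model (2)'s own rows is -0.77, so much of the gap from -0.43 reflects a different group.

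**The case against.** The strongest reply is that conditioning on the latest score is deliberate. Some components are offered only on elevated scores, so what happens next to a currently symptomatic patient is a fair clinical question. That stands, and it is why model (2) should stay. It does not make the exposed and unexposed rows comparable.

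The size is also open to challenge. One point on average is large beside the 0.10-0.20 points in the Power Statement. If all benefit fell on elevated rows, and these were 34% of control surveys (as in pattern (a) of the simulation, not a document figure), 0.10-0.20 overall would be 0.10/0.34 = 0.29 to 0.20/0.34 = 0.59 points in those rows. Depletion there lies between undetectable and roughly 20%. This stands.

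A reader might infer that the symptomatic group fills with patients E2C2 has failed and that the effect is therefore understated. The documents do not support this. The group also holds new onsets, relapses, new entrants and first post-go-live surveys whose prior score was unexposed, and non-response can lead to Level 2 care. Patterns (c) and (d) give the opposite direction.

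The fallback's rule keeps responders in the group, but it applies only if model (2) fails, and entry into it can still depend on exposed scores.

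Finally, the first score is not a clean baseline for everyone. Hypotheses H1a concedes that the intervention may affect it, so any fixed-group rule must provide for patients who enter after go-live.

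**Conclusion.** The point holds as a matter of design. Model (2) defines H1b's group by scores the intervention is meant to change, and the plan has no H1b analysis with a fixed group.

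The estimate is understated if benefit lasts and only some patients respond. It can exceed the fixed-group effect if benefit acts only after an elevated score. With no intervention effect, membership is not altered by exposure and there is no bias, so this is not a false-positive problem.

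The sizes rest on assumed means, variances, correlations and response patterns, for one symptom, without cluster effects, deaths or survey non-response. They show direction and order of magnitude, not a forecast. They are separate from the attenuation caused by adjusting for an exposed prior score.

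The fixed group is a comparator, not a gold standard. Its fit was within 0.06 of the true fixed-group effect in patterns (a) to (d), but 0.15 short in (e). This is a cheap improvement that settles what H1b can conclude, not a fatal flaw.

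**What to change.** Beside model (2), pre-specify an H1b sensitivity analysis:

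- Set E_ik = 1 if the patient's first score (j = 1) for that symptom is above 3, and interact it with X.
- Adjust for the first score instead of the prior score. Include the lag since that score and its interaction with it, as the survey-level robustness models under Hypotheses H1a already do. Let the lag also interact with E_ik, because exposed surveys tend to come later after the first score.
- Report D_i and B_i + D_i for this model and for model (2).
- Repeat the analysis in patients whose first score precedes their cluster's go-live.
- Describe the model (2) group as *symptomatic at the previous visit, after any earlier E2C2 exposure*, and reconcile it with the ever-elevated wording in Specific Aim 1 Analyses and the any-prior rule in the fallback.

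The cost is one or two more model fits on data already collected, plus SAP wording. The fixed group leaves out symptoms that start later and becomes less current over long follow-up, so it supplements model (2) and does not replace it.
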